8.3.2 WHO Clinical Progression Scale

A study team member will complete the WHO Clinical Progression Scale (Appendix 4) during participant contact sessions via telephone, text/direct messaging, web-based conference, or in person on relevant study days as detailed in the SOE (Section 1).

8.4 Biohazard Containment

Precautions will be employed by all personnel in the handling of specimens collected during this study. All dangerous goods and materials, including diagnostic specimens and infectious substances, must be transported using packaging mandated by national and regional regulations.

Details of these procedures will be described in the Laboratory Manual and will comply with relevant IATA Dangerous Goods Regulations.

9. SAFETY MONITORING

9.1 Responsibilities for Ensuring the Safety of Study Participants

9.1.1 Principal Investigator

The Principal Investigator has a personal responsibility to closely monitor study participants and an inherent authority to take whatever measures necessary to ensure their safety, including ensuring that procedures and expertise are available to cope with medical emergencies during the study. The Principal Investigator has the authority to terminate, suspend or require changes to a clinical study for safety concerns and may pause or delay the administration of the study drug to an individual or across the study if they have concerns that the study drug may place participants at significant risk.

9.1.2 Study Sponsor

The Sponsor has an institutional responsibility to ensure participant safety and undertakes to promptly notify the concerned Investigators, IRB/EC(s) and the Regulatory Authority of findings that could adversely affect the safety of participants included in the study, impact the conduct of the study, or alter the IRB/EC's approval of, or favourable opinion to continue, the study. This includes the expedited reporting to these parties of all adverse drug reactions that are both serious and unexpected.

9.1.3 Study Funder

The Funder (BMGF) and/or [name] company has a responsibility to immediately inform the Sponsor and Principal Investigator of any new information related to the study drug or its

intended use which could alter the existing risk assessment of the study or could adversely affect participant safety.

9.1.4 Medical Monitor

The Medical Monitor, in consultation with the Safety Review Team (SRT), will provide medical review during the execution of the study. This oversight will include the review of safety information and the provision of applicable recommendations to both the Investigator and the Sponsor. This review is intended to facilitate the early detection of safety signals and to maximise the chances for the continued appropriateness of the study and the protection of the study participants. Medical review of data will be specified in detail in the medical section of the Medical Monitoring Plan to be finalised prior to enrolment of the first participant.

In addition to routine review of medical data, the Medical Monitor will also support the site and provide advice on protocol clarifications, assessment of eligibility and required follow-up procedures as and when requested by the Investigator.

The Medical Monitor, in conjunction with the Principal Investigator, will be responsible for adjudication of the primary endpoint events of hospitalisations and deaths to ascertain if these are/were COVID-19 related.

9.1.5 Safety Review Team

The SRT will comprise at least the following personnel:

- the Principal Investigator
- the Medical Monitor
- the Safety Physician
- another medically qualified physician, virologist, or immunologist.

The members of the SRT are responsible for decisions relating to participant safety and study continuation.

The timing of other SRT data reviews and a detailed description of the operational aspects of the SRT will be documented in the SRT Charter.

9.1.6 Data and Safety Monitoring Board

An independent Data and Safety Monitoring Board (DSMB) will be convened for this study with expertise in COVID-19 or respiratory viruses, and emerging epidemics. A biostatistician will also form part of the DSMB. The purpose of the DSMB is to monitor the study for safety and operational futility. The board will provide recommendations to the Sponsor regarding ongoing study conduct.

In addition to meeting at pre-determined, scheduled time points, the DSMB will also be called upon to perform evaluations of relevant data should any of the study pause criteria be met at any stage, and to make recommendations about study stopping or continuation, or amended circumstances under which the study may proceed.

The objectives and responsibilities of the DSMB, and the DSMB operational procedures will be detailed in the DSMB Charter which will be ratified by the DSMB members prior to study start.

9.2 Adverse Events

9.2.1 Definitions

The following definitions are based on those described in the SAHPRA Safety Reporting Guidelines for Clinical Trials conducted in South Africa²².

An **adverse event (AE)** is any untoward medical occurrence in a patient or clinical trial participant administered an investigational product that may present during treatment with that investigational product, but which does not necessarily have a causal relationship with this treatment.

A **treatment emergent adverse event (TEAE)** is any new AE that begins, or any pre-existing condition that worsens in severity, after at least one dose of study product has been administered.

An **adverse drug reaction (ADR)** is a response to a medicine in humans which is noxious and unintended, and which occurs at any dose, and which can also result from overdose, misuse, or abuse of a medicine. "Response" in this context means that a causal relationship between a medicine and an adverse event is at least a reasonable possibility.

A **serious adverse event (SAE)** is defined as any untoward medical occurrence that:

- Results in death (including from COVID-19)
- Is life-threatening (the term "life-threatening" in the definition of "serious" refers to an event in which the participant was at immediate risk of death at the time of the event; it does not refer to an event which hypothetically might have caused death if it was more severe)
- Requires inpatient hospitalisation or prolongation of existing hospitalisation (including for COVID-19) unless this is for:
 - elective or pre-planned treatment for a pre-existing condition that is unrelated to the trial and has not worsened since the start of the investigational product
 - treatment on an emergency outpatient basis for an event not fulfilling any of the definitions of an SAE given above and not resulting in hospital admission
 - cosmetic surgery or for social reasons or respite care in the absence of any deterioration in the participant's general condition
- Results in persistent or significant disability/incapacity
- Results in a congenital anomaly/birth defect
- Is medically significant or important event or reaction.

An **Unexpected Adverse Drug Reaction** is one in which the nature, specificity, severity, and outcome is not consistent with the applicable product information (i.e., with the Summary of Product Characteristics [SmPC] or the Investigator's Brochure). An expected ADR with a fatal outcome should be considered unexpected.

A **suspected unexpected serious adverse reaction (SUSAR)** is an unexpected adverse drug reaction which also meets the criteria for a serious adverse event.

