3. OBJECTIVES AND ENDPOINTS

Primary	
Objectives	Endpoints

To evaluate the effectiveness of molnupiravir compared to placebo in preventing severe	
Combination of incidence of COVID-19-related hospitalisation (≥ 24 hours of care in a hospital)

disease progression in adults with mild COVID-19
 
 • To evaluate the safety of molnupiravir in adults with mild COVID-19 	
or similar acute care facility) and COVID-19-related mortality to Day 29
 
 • Adverse events (including serious adverse events and adverse drug reactions) • Self-assessed vital signs to Day 10

Secondary
	

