10.1 Sample Size Determination

This study has been powered around a reduction from 6% to 4% in hospitalisation/death rates between the arms. This would give a 33% reduction, the approximate effect size seen in the registration MOVE-OUT trial¹².

With 1863 patients per arm, there would be 80% power to detect a reduction in hospitalisations from 6% to 4% in a single final analysis. A 5% overage to account for loss to follow up has been added, resulting in a total sample size of 2000 patients per arm. The interim (e.g., at 1000/arm) would need to use a Peto rule ($p<0.001$) to preserve statistical power for the final analysis.

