10.3.5 Safety data

All safety analyses will be performed for the SAF.

An overall summary of the number of participants with any AE, AEs considered related to study drug, SAEs, SAEs considered related to study drug, AEs leading to withdrawal of study drug, and AEs leading to withdrawal from the study will be presented.

AEs will be coded in accordance with MedDRA. The most recent released version of MedDRA at the time of study start will remain in effect throughout the study.

AEs will be summarised by MedDRA primary system organ class and preferred term. Summaries will be presented for overall incidence (number of participants and number of events), as well as by severity and relatedness to study drug.

Vital signs will be summarised. Absolute values and change from baseline will be presented.

All safety data will be listed.

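### The all-SAE summary includes the primary effectiveness events, so at the planned effect it favours molnupiravir by about 40 participants and needs a companion count without COVID-19 events

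*Protocol*

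**What the plan says.** Section 3 has two primary objectives. For effectiveness the endpoint is "Combination of incidence of COVID-19-related hospitalisation" (at least 24 hours of care) together with COVID-19-related mortality, to Day 29. For safety the first endpoint listed is "Adverse events (including serious adverse events and adverse drug reactions"). Section 9.2.2.1 collects AEs and SAEs up to the Day 29 visit, so both endpoints cover the same follow-up.

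Section 9.2.1 makes the overlap explicit. An event is serious if it "Requires inpatient hospitalisation or prolongation of existing hospitalisation (including for COVID-19) unless this is for" certain exceptions (elective or pre-planned treatment, outpatient emergency treatment, social reasons), none of which removes a COVID-19 admission. COVID-19 deaths are likewise named under the death criterion.

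Section 10.3.5 plans "An overall summary of the number of participants with any AE, AEs considered related to study drug, SAEs, SAEs considered related to study drug", plus AEs leading to withdrawal of drug or from the study. It adds tables by system organ class, preferred term, severity and relatedness, and full listings. None of the listed summaries separates COVID-19 progression from other serious events.

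The information needed to separate them will exist. Section 9.1.4 makes the Medical Monitor, with the Principal Investigator, "responsible for adjudication of the primary endpoint events of hospitalisations and deaths to ascertain if these are/were COVID-19 related".

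**The concern.** If molnupiravir prevents COVID-19 admissions and deaths, it also lowers the number of participants with an SAE. A lower or equal SAE total on molnupiravir then has two readings: the drug causes no serious harm, or the harm it causes is offset by the admissions it prevents. The all-SAE line cannot tell these apart, and it is the line most readers would turn to for the primary safety objective.

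The exposed case is an excess of serious events that investigators, one case at a time, judge unrelated. Participants are 50 or older, with a listed comorbidity unless they are 65 or older, and all have COVID-19, so another explanation will often be at hand. A randomised comparison of totals is the tool that would normally reveal such an excess. No scheduled safety laboratory tests are planned (8.2.4.1), so clinical events carry most of the safety evidence.

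**Working it through.** **Inputs from the protocol.** Section 10.1: "This study has been powered around a reduction from 6% to 4% in hospitalisation/death rates between the arms"; 1863 per arm for 80% power; 2000 per arm enrolled. Allocation is 1:1 (6.1.2).

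**Assumptions.** Two-sided alpha of 0.05, which 10.1 does not state. The 6% and 4% are taken as rates of the COVID-19-related primary endpoint. Nearly all of those events are taken to meet the SAE definition. The protocol gives no rate of other SAEs, so a background *b* in both arms and an excess *e* on molnupiravir are assumed and varied. No participant has both kinds of event.

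**Step 1. The plan's own figure.** With pooled variance and no continuity correction:

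n = [1.960·√(2·0.05·0.95) + 0.842·√(0.06·0.94 + 0.04·0.96)]² / 0.02² = (0.6041 + 0.2591)² / 0.0004 = 1863.

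This matches 10.1, so 6% and 4% are the rates in use.

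**Step 2. The built-in offset.** Placebo: 0.06 × 2000 = 120. Molnupiravir: 0.04 × 2000 = 80. Difference: 40 participants, or 40/2000 = 2.0 percentage points. With 1863 per arm the difference is 0.02 × 1863 = 37. The offset equals the risk difference times the arm size, so half the planned effect would give 20 and no effect would give none.

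**Step 3. What the total would show.** All-SAE risk is 6% + *b* on placebo and 4% + *b* + *e* on molnupiravir. The last two columns give the chance that a two-sided 5% comparison of two proportions (normal approximation) shows a significant excess on molnupiravir. The protocol plans no such test; they only measure how visible the excess is.

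| *b* | *e* | Other SAEs, placebo v drug | All SAEs, placebo v drug | Without COVID-19 events | All-SAE total |
|---|---|---|---|---|---|
| 0.5% | 1 point | 10 v 30 | 130 v 110 | 89% | 0.05% |
| 1% | 1 point | 20 v 40 | 140 v 120 | 74% | 0.06% |
| 2% | 1 point | 40 v 60 | 160 v 140 | 53% | 0.08% |
| 0.5% | 2 points | 10 v 50 | 130 v 130 | over 99% | 2.5% |
| 1% | 2 points | 20 v 60 | 140 v 140 | 99% | 2.5% |
| 2% | 2 points | 40 v 80 | 160 v 160 | 96% | 2.5% |

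The row with *b* = 1% and *e* = 1 point in full:
- Without COVID-19 events: SE under no difference = √(2·0.015·0.985/2000) = 0.00384; SE under the alternative = √[(0.01·0.99 + 0.02·0.98)/2000] = 0.00384; Φ[(0.01 − 1.96·0.00384)/0.00384] = Φ(0.64) = 74%.
- All SAEs: both SEs are 0.0078; Φ[(−0.01 − 1.96·0.0078)/0.0078] = Φ(−3.24) = 0.06%.

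**Step 4. The same row as risk ratios** (molnupiravir over placebo, SE of the log ratio = √(1/a + 1/c − 2/2000), where a and c are the two arms' counts):
- Other SAEs: 40/20 = 2.00, SE = √(1/40 + 1/20 − 0.001) = 0.272, 95% CI 1.17 to 3.41.
- All SAEs: 120/140 = 0.86, SE = √(1/120 + 1/140 − 0.001) = 0.120, 95% CI 0.68 to 1.09.

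A doubling of other serious events would thus sit behind an all-SAE ratio below 1.

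**The case against.** **Counting these events as SAEs is not an error.** A reader might infer that 9.2.1 is wrong. It is a reporting definition, which the protocol bases on the national regulator's safety guideline, and reporting an event is separate from analysing it. This stands, and the definition should not change.

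**Other outputs are not cancelled.** A reader might also infer that efficacy could hide any drug-related excess of serious events. The protocol does not support that. Related SAEs have their own line in 10.3.5, and relatedness under 9.2.2.3 extends to possibly related events. One related SAE halts enrolment (4.3). AEs are tabulated by organ class, preferred term, severity and relatedness, and listed. Section 9.2.2 asks that symptoms be grouped into one diagnosis where possible, which limits how far COVID-19 progression scatters over terms. This stands and narrows the point to the all-SAE total, and in part the any-AE total. An excess judged unrelated would still appear in the preferred-term tables, though possibly as small counts spread over several terms.

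**No decision hangs on the total.** Section 10.3.5 is descriptive, states no SAE test and does not mention arms; comparison by arm is inferred from the placebo-controlled design. This stands too: the weakness is one of interpretation and does not make a test invalid.

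**The SAP may add the split.** It may, since section 10 leaves detail to it. But 10.3.5 sets out its own list of safety summaries, whereas 10.3.4 and 10.3.6 simply defer to the SAP. If the SAP already contains the split, the point is met.

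**The illustrative rates are assumed.** Correct. Only the offset of 120 against 80 comes from the protocol.

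**Conclusion.** The point holds in a limited form. The all-SAE summary for the primary safety objective contains the primary effectiveness events. At the planned 6% against 4% of 2000 per arm it favours molnupiravir by about 40 participants, so an excess of other serious events of up to about 2 percentage points that investigators judge unrelated would leave that total equal or lower on molnupiravir. A larger excess would still raise the total.

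This assumes that the planned effect occurs, that nearly all effectiveness events qualify as SAEs, and that few participants have both kinds of event. The two definitions are not identical: the endpoint requires at least 24 hours of care in a hospital or similar facility, whereas the SAE criterion requires inpatient admission. Whether an excess of other SAEs exists, and how large, cannot be judged from the protocol.

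The documents do not support a conclusion that the safety evaluation as a whole is masked, or that recognised drug-related events could be cancelled.

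**What to change.** Keep the SAE definition in 9.2.1 and the all-SAE summary in 10.3.5 as they are. Add one sentence to 10.3.5, for example: *SAEs and deaths will be summarised by treatment arm for all events and, beside this, with hospitalisations and deaths adjudicated as COVID-19-related under Section 9.1.4 left out; the two summaries will be interpreted together.* The DSMB should see both.

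The addition should stay limited to SAEs and deaths. Section 9.1.4 adjudicates only hospitalisations and deaths, so a matching version for all AEs cannot be built from it, and SAEs that are serious on other grounds stay in both summaries.

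The cost is one sentence and one repeated table, using an adjudication already required. The drawback is that the second summary rests on a judgement made after randomisation, albeit in a double-blind trial. A deterioration caused by the drug but attributed to COVID-19 would drop out of it. The safety conclusion should therefore not rest on the second summary alone, and the all-event summary stays beside it.

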9.2.2 Assessment and recording of adverse events

All AEs regardless of seriousness or relationship to the study drug are to be recorded in the eCRF. AEs can be spontaneously reported by the participant, observed by the Investigator (either directly, or through an objective assessment) or elicited by general questioning. Whenever possible, symptoms should be grouped as a single syndrome or diagnosis.

The following information should be recorded for each AE:

- a description of the adverse event (verbatim term)
- the dates of onset and resolution of the event (and whether the event started prior to or after start of study drug)
- the characteristics of the event (seriousness, severity)
- the action taken in response to the event (including treatment required)
- the outcome of the event
- the relationship of the event to the study drug (causality assessment).

Vital signs abnormalities are to be recorded as AEs only if they are considered clinically significant, are symptomatic, require corrective treatment or fulfil a seriousness criterion. Day-to-day fluctuations in pre-existing conditions that do not represent a clinically significant change in the participant's status (including fluctuation in symptoms of mild COVID-19) will not be reported as AEs.

9.2.2.1 Reporting time period

For the purpose of this study, all non-serious AEs will be reported from the time of granting main study informed consent until the participant's EOS visit (Day 29). Events reported prior to this will be recorded as medical history unless the symptoms worsen during the follow-up period.

SAEs will be reported for the same period. SAEs occurring after the reporting period that the Investigator becomes aware of will only be reported to the Sponsor if the Investigator suspects a causal relationship with the study intervention.

9.2.2.2 Severity grading

The medical assessment of AE severity will be recorded in accordance with the classification detailed in the Division of AIDS (DAIDS) Table for Grading the Severity of Adult and Paediatric Adverse Events Version 2.1, Jul 2017²³..

AEs not specifically referenced in the DAIDS classification will be graded in accordance with the following general guidelines detailed in the classification document:

- Grade 1: Mild symptoms causing no or minimal interference with usual social and functional activities with intervention not indicated
- Grade 2: Moderate symptoms causing greater than minimal interference with usual social and functional activities with intervention indicated
- Grade 3: Severe symptoms causing inability to perform usual social and functional activities with intervention or hospitalisation indicated
- Grade 4: Potentially life-threatening symptoms causing inability to perform basic self-care functions with intervention indicated to prevent permanent impairment, persistent disability, or death
- Grade 5: Death related to the AE.

9.2.2.3 Relationship to study drug

The Investigator must assess the relationship of each event to the study drug and decide whether, in his or her medical judgment, there is a reasonable possibility that the event may have been caused by the study drug. This should be documented in the participant's source documentation and eCRF.

The following may guide this assessment:

- Related:
 - The event has a reasonable temporal relationship to study drug administration
 - The event is more likely to be explained by the study drug than by another cause
 - This includes events considered possibly related to the study drug
- Not related:
 - Events not meeting the “related” criteria.

Where possible, a distinction should be made between events considered related to the study drug and those related to study-specific procedures.

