4.3 Study Pausing Rules

The occurrence of any serious adverse event (SAE) considered related to the study drug will prompt a halt to further enrolment into the trial pending a formal safety review by the DSMB.

Dosing of on-study participants, and follow-up of participants previously enrolled and dosed, will not be altered unless, for example, additional safety measures are judged to be required following the safety review.

The DSMB will provide recommendations to the Sponsor regarding study stopping or continuation or amended circumstances under which the study may proceed as detailed in the DSMB Charter. Additional investigations or assessments may be recommended to establish causality or ensure ongoing safety of enrolled participants.

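### One guidance bullet in protocol section 9.2.2.3 sets a higher bar for calling an event related than the rest of that section and the ADR definition, so some events can be coded either way

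*Protocol*

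**What the plan says.** Section 9.2.2.3 opens with a mandatory judgement by the investigator: whether "there is a reasonable possibility that the event may have been caused by the study drug". It then offers aids to that judgement, introduced by "The following may guide this assessment". Three bullets stand under the related category:

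- The first asks for plausible timing relative to dosing.
- The second compares the drug with other explanations: "The event is more likely to be explained by the study drug than by another cause".
- The third widens the category to cover weaker links: "This includes events considered possibly related to the study drug".

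The only other category is defined by exclusion: "Events not meeting the “related” criteria".

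Section 9.2.1 defines an adverse drug reaction as a response for which "a causal relationship between a medicine and an adverse event is at least a reasonable possibility".

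The classification is used elsewhere. Section 3 names ADRs within the primary safety endpoint. Section 10.3.5 tabulates related AEs and related SAEs. Section 9.2.2.5 continues follow-up beyond the end-of-study visit for related AEs that are still ongoing. Section 4.3 makes a single event sufficient to pause recruitment: "The occurrence of any serious adverse event (SAE) considered related to the study drug will prompt a halt to further enrolment".

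**The concern.** The protocol asks for one yes-or-no decision and describes its threshold in ways that do not agree. A reasonable possibility and possibly related are low bars. Being likelier than another cause is a comparative and higher bar.

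The gap matters here because every participant has an illness that offers a competing explanation. Section 2.2.2.2 lists diarrhoea, nausea and dizziness as the most common adverse reactions. Inclusion criterion 5 in section 5.1 lists nausea and diarrhoea as COVID-19 symptoms, and the questionnaire in Appendix 2 scores nausea, dizziness and diarrhoea as symptoms of the illness. An investigator guided by the second bullet could code such an event not related; one guided by the lead sentence or the third bullet could code it related. In a multi-centre trial, sites may split on this, and the number of related events then has no fixed meaning. The pausing rule is the most sensitive use, because one SAE labelled related is enough.

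**Working it through.** The protocol states no figure for causality or for how often the pausing rule would act, so there is nothing to reproduce. The check is a comparison of texts.

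**Step 1. Put one event through each statement.** Take an event with plausible timing that the drug could have caused, but for which another cause is likelier.

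| Statement | Standard | Result for this event |
|---|---|---|
| 9.2.2.3, lead sentence (mandatory) | reasonable possibility | related |
| 9.2.2.3, bullet 1 (guidance) | plausible timing | met |
| 9.2.2.3, bullet 2 (guidance) | drug likelier than another cause | not met |
| 9.2.2.3, bullet 3 (guidance) | possibly related is included | related |
| 9.2.2.3, other category | fails the related criteria | depends on whether bullet 2 counts |
| 9.2.1, ADR | at least a reasonable possibility | ADR |

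**Step 2. Find the source of the conflict.** The lead sentence, bullet 3 and section 9.2.1 agree. Bullet 2 alone departs from them. The conflict with the ADR definition therefore comes from one bullet, not from the section as a whole.

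**Step 3. Ask whether the text resolves it.** The list does not say whether its criteria apply jointly. If bullet 2 must be met, the event falls into the excluded category, and bullet 3 admits events that bullet 2 has just shut out. If bullet 3 overrides, bullet 2 has no effect on exactly the events where it would matter. There is no intermediate category to absorb the difference.

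**Step 4. Trace what depends on the code.**

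- Exposed: the ADR or related part of the safety endpoint (section 3), the related AE and related SAE summaries (10.3.5), follow-up of related AEs after end of study (9.2.2.5), and the enrolment halt (4.3).
- Not exposed: total AEs and total SAEs. Section 9.2.2 has every AE recorded whatever its relationship to the drug, and 9.2.3 has every SAE reported to the sponsor within 24 hours.

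**Step 5. Consider direction.** Section 6.1.3 keeps the assessor of AEs blinded to treatment. The ambiguity therefore bears on both arms. It affects the level and meaning of the related counts and the chance of a halt; it does not by itself favour one arm.

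**The case against.** The best defence is that the text largely settles the matter. The sentence with mandatory force uses the same standard as the ADR definition, the bullets are only optional aids, and bullet 3 says where borderline events go. Three statements point to the inclusive reading and one guidance bullet points away. This is a fair limit on the finding, but it does not dispose of it. Bullet 2 is listed as a criterion for the related category, and the other category is defined by failing those criteria, so an investigator who relies on bullet 2 is following the protocol.

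Several stronger readings are tempting, and the documents do not support them.

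- A reader might infer that an event is related solely when the drug is the likelier cause. No text says so; the mandatory sentence and bullet 3 say otherwise.
- A reader might infer that the whole primary safety count is unstable. Only the related or ADR subset is, for the reasons in step 4.
- A reader might infer that known reactions would go unreported. They would still be recorded; they could only be under-labelled as related. Some overlap with the illness is also removed, because section 9.2.2 does not report fluctuation in mild COVID-19 symptoms as AEs.
- A reader might infer that expedited reporting fails. Section 9.1.2 ties it to adverse drug reactions, a term defined in 9.2.1 and not by the disputed bullet. Section 9.2.3 also requires enough detail on every SAE for an independent view of causality.
- A reader might try to size the problem from reaction rates in the earlier phase 3 trial or from the planned number of hospitalisations and deaths. Neither measures how many events here would be borderline, and each SAE needs a causality judgement under any wording.

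**Conclusion.** The point holds as an internal inconsistency in a stated rule. Bullet 2 of section 9.2.2.3 sets a higher bar than the section's own lead sentence, its third bullet and section 9.2.1, so an event that is possible but less likely to be due to the drug can be coded either way.

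The size cannot be computed: the documents give neither the share of events in this zone nor the share that investigators would call related. The conclusion assumes only that some events will have both a plausible link to the drug and a likelier alternative cause, which the overlap between listed reactions and COVID-19 symptoms makes reasonable. The reach is confined to the four uses listed as exposed, and no between-arm bias is shown.

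It should be corrected in the protocol. Investigators make the judgement event by event, and a later analysis plan cannot recover which bullet each of them applied.

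**What to change.** Reconcile sections 9.2.2.3, 9.2.1 and 4.3 to one stated causality threshold. The smallest edit is to remove or reword bullet 2 so that the guidance agrees with the reasonable-possibility standard already stated in 9.2.1 and in the lead sentence of 9.2.2.3. Then refer to that same threshold in the pausing rule (4.3) and in the safety summaries (10.3.5), so that related means one thing throughout.

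The direct cost is one edited bullet and a training note to sites. There is also a consequence to accept knowingly: more events may be labelled related and, because one related SAE is enough, the enrolment halt may be triggered more often. The sponsor and the DSMB should be aware of this when the wording is settled.
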